Yohimbine: Patients will receive a single oral dose of 32.4mg yohimbine or yohimbine-matched placebo in the lab, approximately one hour prior to the cue reactivity procedure, which correspond to the yohimbine time to reach maximum concentration (t_{max} =1 h). Yohimbine 32.4mg is based from multidose yohimbine administration to heroin-dependent/buprenorphine stabilized volunteers which increased opioid-seeking behaviors (15). The PI has already obtained an IND from the FDA for the use of yohimbine in this study and she is currently using this same oral dose in another trial funded via her K01 (NCT: 02243709; IND: 121984)]. Further supporting the safety of yohimbine, other prior studies have used yohimbine to examine neuroendocrine probes to boost stress signal in human studies (20, 22, 109). Ample data support the safe use of yohimbine to induce craving in alcohol-dependent individuals (22), and the safe induction of stress in PTSD veterans (110) and gamblers (96).

Telephone prescreening (Attachment J)

Visit 1 (Screening) Before starting any procedure the participant will sign the Consent document (**Attachment K**). Participants will be assessed on inclusion/exclusion criteria according the CADRE psychometric scales, vital signs, ECG, blood, saliva and urine analysis standardized format. Specific for this project, we will include an additional blood analysis ensure the presence of buprenorphine and absence of opioids. Females will report their last menses and the use of hormone-based contraceptives (111).

Visit 2 (Randomization) – Day 1 After medical clearance, blood will be collected for clinical laboratory tests to assess basal β-endorphin, and other stress hormones (neurotensin, orexins and substance P) during five visits (Visit 1, 3, 4, 5 and 6) (one vial). Basal salivary oxytocin and cortisol will be collected by passive drooling (one vial). Since oxytocin has shown to decrease cortisol release and anxiety in response to social stress (6), samples of salivary cortisol will be collected at three time points (stress induction, cue reactivity and end of the experiment) to measure cortisol levels as a biomarker of oxytocin's effect on acute stress. Then, participants will be randomized to either oxytocin or oxytocin-matched placebo group that will be dispensed as a nasal spray and the session will include a 30 min

discussion of the proper administration of the nasal spray, the potential side effects and drug-drug interactions.

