Visit 3 (Laboratory Session I) – Day 5 Participants will provide a urine sample (drug toxicology), and a one vial blood sample (β -endorphin, hormone levels). Participants will then complete a series of assessments (**Table 1**) and receive a single oral dose of yohimbine or yohimbine-matched placebo. Fifteen minutes later, participants will administer a dose of oxytocin or oxytocin-matched placebo (40 IU, 4 sprays per nostril), after 30 min the first sample of saliva (cortisol and oxytocin) will be collected and the cue-reactivity will begin (112). Cue-Reactivity (CR) Task will be administered in a similar manner to other published studies (72, 73) for individuals with OUD with cues selected based on patients' drug experience. To measure cue-induced opioid craving, participants will a view images of neutral stimuli and then of opioid drug use (24). Participants will rate their craving via drug visual analog scale (VAS) and the second sample of saliva cortisol will be collected (45 min later). Vital signs will be monitored during the entire procedure. Participants will then complete Post-Cue measures, will have their vital signs measured and conduct the last sample of saliva.

Visit 4 (Laboratory Session II) – Day 7 Participants will come back after two days. The procedure will be similar to Visit 3 but they will receive the opposite condition (yohimbine or yohimbine-matched placebo).

A two-day washout period will occur followed by initiation of the opposite intranasal medication condition (i.e. oxytocin and oxytocin-matched placebo) to be administered for one week starting at day 9.

Visit 5 (Laboratory Session III) – Day 14 Participants will complete the lab procedures as described in Visit 3 and 4, however, this time will be administered the opposite oxytocin condition (i.e. oxytocin or oxytocin-matched placebo). Participants will also receive yohimbine or yohimbine-matched placebo (counterbalanced).

Visit 6 (Laboratory Session IV) – Day 17 Participants will come back after two days. The procedures will be completed as described in Visits 3-5, but they will receive the opposite condition (yohimbine or yohimbine-matched placebo).

Visit 7 (follow-up) – Day 20 After three days, participants will come to the lab for the final assessments (Table 1).

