Outcomes: Primary (craving) and secondary (safety and tolerability) outcomes were assessed in realtime in the laboratory. Seven-day oxytocin administration was compared to the oxytocin-matched placebo condition during the CR procedure, in which noradrenergic activation produced by yohimbine or yohimbinematched placebo condition (2X2 design) was measured. We used Generalized Linear Model (GLM) with modelbased estimator in the covariance matrix, with medication (oxytocin/placebo) and noradrenergic activation (yohimbine/placebo) as within-subject factors. The model was specified to evaluate the effect of drug (oxytocin/placebo) by noradrenergic (vohimbine/placebo) interaction, main effect of the drug, and main effect of noradrenergic activation. Craving was assessed using the DDQ with time coded as: t_0 =relaxation, t_1 =interaction with drug paraphernalia/opioid auditory cues and t_2 =opioid use video. Safety and tolerability were assessed using: SBP, DBP, HR (vital signs), HAM-A and STAI (anxiety). The STAI y1 (state) was included as an additional safety measure for anxiety to ensure participants were not experiencing acute symptoms of anxiety within the laboratory. The STAI y2 (trait) was inserted as a covariate in the model to control for baseline anxiety level, along with stress (PSS), HPA (cortisol), and noradrenergic response (α -amylase). Time at laboratory sessions was coded as: t_0 =baseline, t_{45min} =45-min after yohimbine administration, and t_{90min} =post cue-exposure to specifically evaluate the contribution of each laboratory procedure (vohimbine and CR). Withdrawal symptoms (COWS) and AEs were assessed at specific timepoints: t_0 =pre-laboratory and t_1 =post-laboratory procedures.

Other outcomes (safety and tolerability) were measured retrospectively during the one-week outpatient setting and included the: COWS (withdrawal), anxiety (HAM-A and STAI), stress (PSS), depression (HAM-D) and AEs. The other outcomes were analyzed using ANOVA test and the number of AEs via a χ^2 test. For missing data approach, we first categorized missing data as missing completely at random (MCAR), missing at random (MAR) or missing not at random (MNAR)⁷. Analysis with GLM (using all available pairs of data to model missing values with maximum likelihood estimation) was deemed suitable for our analyses because no systematic differences existed between participants with missing data and those with complete data (MCAR)⁸.

Missing data reporting ⁹

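### The SAP adjusts for stress (PSS), cortisol and alpha-amylase without limiting them to pre-treatment values or saying which models contain them

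*SAP*

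**What the plan says.** **SAP, Statistical analysis, outcomes paragraph.** The generalized linear model has oxytocin, yohimbine and their interaction as within-subject terms. After the safety measures are introduced, trait anxiety (STAI) is said to have been "inserted as a covariate in the model to control for baseline anxiety level, along with stress (PSS), HPA (cortisol), and noradrenergic response", with alpha-amylase named as the marker of that response. No sampling time is given for the last three covariates, and the model they enter is not identified. Session times are coded as a baseline, "45-min after yohimbine administration", and after cue exposure. The same paragraph says that "noradrenergic activation produced by yohimbine or yohimbinematched placebo condition (2X2 design) was measured". PSS also appears as an outcome in its own right, among those "measured retrospectively during the one-week outpatient setting and included the: COWS (withdrawal), anxiety (HAM-A and STAI), stress (PSS" and depression.

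**Protocol, Part III, section 3.** The Visit 2 text provides for a basal saliva sample, and for three session samples of cortisol "to measure cortisol levels as a biomarker of oxytocin's effect on acute stress". At Visit 3, yohimbine or its placebo is given first. "Fifteen minutes later, participants will administer a dose of oxytocin or oxytocin-matched placebo", and "after 30 min the first sample of saliva (cortisol and oxytocin) will be collected and the cue-reactivity will begin".

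**Protocol, Part III, section 2.** The exploratory aims treat session cortisol as an outcome compared between oxytocin and placebo. Aim 2 concerns stress at baseline.

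The protocol text gives no schedule for PSS or alpha-amylase. One may exist in attachments that are not shown.

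**The concern.** A covariate measured before treatment can sharpen a treatment contrast without changing what it estimates. A covariate that treatment has already altered is different. Adjusting for it takes out whatever part of the effect passes through it. If something unmeasured drives both the covariate and the outcome, the adjustment can also introduce bias that randomisation does not remove.

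The variables here lie on the stress pathway through which the protocol expects oxytocin to act, or mark the response that yohimbine is meant to provoke. If on-treatment values are used, the oxytocin and yohimbine contrasts become effects net of those pathways. As written, a reader of the results could not tell which kind of effect is reported.

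**Working it through.** **1. The plan's own figure.** The documents give no figure for the effect of this adjustment. The nearest is N = 67 in Protocol Part III, section 4 (ANCOVA, f = 0.35, two groups, three covariates, α = 0.05). It reproduces: noncentrality 0.35² × 67 = 8.21, degrees of freedom 1 and 67 − 2 − 3 = 62, power 0.805. It does not bear on when covariates are measured.

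**2. Session saliva against dosing (Visit 3).** The spray comes 15 min after yohimbine and the first saliva 30 min later: 15 + 30 = 45 min after yohimbine. The second is placed 45 min later; counted from the first, that is 45 + 45 = 90 min. These two agree with the SAP's 45- and 90-minute codes. No session saliva is described before dosing.

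**3. Session baseline.** Visit 3 falls on Day 5 of spray use. The second spray period starts on Day 9 and its first session is Day 14, 14 − 9 = 5 days later. A session t0 value therefore precedes yohimbine but not the spray, in either period.

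**4. Covariate by covariate.**
- STAI trait: Table 1 lists it at screening only. No problem.
- Alpha-amylase: described as a response, in a model whose yohimbine factor is noradrenergic activation. This most naturally means a post-challenge value.
- Cortisol: basal samples exist, but the session samples follow both drugs and are named as a marker of oxytocin's effect.
- PSS: Aim 2 and the baseline battery fit a pre-dose value; the SAP's list of outpatient-week outcomes fits an on-treatment one.

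**5. What on-treatment adjustment would do.** In a linear model with no unmeasured common cause:

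adjusted effect = total effect − Σ (slope of craving on covariate × treatment effect on covariate).

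Every input here is assumed: total oxytocin effect after yohimbine −0.50, total yohimbine effect +0.50, slope 0.25 for each covariate.
- Pre-dose covariates, or slope 0: no change.
- Alpha-amylase +1.0 with yohimbine only: oxytocin stays −0.50; yohimbine 0.50 − 0.25 × 1.0 = 0.25.
- PSS and cortisol −0.3 each on oxytocin: −0.50 + 2 × 0.25 × 0.3 = −0.35.
- The same, plus cortisol +0.5 and alpha-amylase +1.0 with yohimbine: oxytocin −0.35; yohimbine 0.50 − 0.125 − 0.25 = 0.125.
- PSS and cortisol +0.3 each on oxytocin: −0.50 − 0.15 = −0.65.

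Large-sample simulation agreed: yohimbine 0.245 in the second case, oxytocin −0.352 in the third, yohimbine 0.122 in the fourth, oxytocin −0.652 in the fifth.

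**6. Unmeasured common cause (assumed).** Suppose treatment shifts a covariate of unit variance by −0.5, the covariate has no effect on craving, and both load 0.5 on a shared unmeasured factor. The spurious slope is 0.5 × 0.5 = 0.25, so −0.50 becomes −0.50 + 0.25 × 0.5 = −0.375, with no mediation at all.

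**7. Precision.** This uses the participant structure in the SAP's missing-data section: 16 crossovers, 4 with one spray condition, 4 without yohimbine. If those last four are split evenly between the two groups, there are 14 × 4 + 2 × 2 + 2 × 2 + 2 × 1 = 66 sessions. With an assumed within-person correlation of 0.5, the standard deviation of the oxytocin estimate without and with on-treatment covariates was 0.278 and 0.272 in the third case, and 0.279 and 0.269 in the fourth. With slope 0 it was 0.252 and 0.264.

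**The case against.** The strongest reply is that this is an unclear sentence, not a wrong analysis. The covariate sentence states one purpose, control for a baseline level, and the other three could be read as sharing it. Aim 2 concerns baseline stress, a basal cortisol sample is described, and the sample-size rationale starts from baseline stress as a predictor and assumes three covariates. That keeps a baseline reading open for PSS and cortisol. It fits poorly with a covariate called a response, and no text says that pre-dose values were used.

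The timing match is also incomplete. Only two of the three saliva samples have SAP codes, the SAP's t0 has no saliva counterpart at Visit 3, and the protocol's yohimbine paragraph puts dosing about an hour before the cue task, not 45 min. Nothing ties the covariates to the session codes. The timing shows what session samples would be, not that they were used.

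A reader might go further and infer that the primary craving result is biased, or biased towards no effect. The documents support neither. The covariate sentence follows the safety measures, so entry into the craving model is not shown. Only cortisol is said to respond to oxytocin; nothing says that alpha-amylase does. The illustrations return whatever slope and shift are assumed, so they can point either way or show nothing. The shift of 0.15 is also about half the standard deviation of the estimate at trial size (0.15 / 0.278 = 0.54).

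**Conclusion.** The concern stands in conditional form and should be fixed. The stated covariate set admits values that treatment can change, and for alpha-amylase most naturally means them. For cortisol and PSS either reading is possible. If on-treatment values enter and treatment moves them, the adjusted contrast is not in general the total effect: cortisol and PSS bear on oxytocin, and alpha-amylase mainly on yohimbine. The interaction is touched by alpha-amylase only if its response to yohimbine differs between spray conditions.

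Neither size nor direction follows from the documents. The change is zero if pre-dose values were used. It is also zero if the covariates are unrelated to craving, apart from treatment, and no unmeasured cause links them. That on-treatment values were in fact used, or that they entered the craving model, is not established.

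**What to change.** State, for each covariate, when it was measured and which models contain it. In every model meant to estimate a total effect, use only values from before the first spray dose:
- STAI trait;
- basal cortisol from screening or Visit 2, as actually collected (the Visit 2 text describes a basal saliva sample, but Table 1 marks no hormone collection at that visit, so the two need reconciling);
- PSS, if it was collected before dosing.

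Leave out session cortisol, session alpha-amylase and on-treatment PSS. Report session cortisol as the exploratory outcome already named. Label any model adjusted for on-treatment values as a secondary mediation analysis.

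The cost is SAP wording, no new data, and a re-run only if on-treatment values were used. Precision may fall slightly if the dropped covariates predict craving: in the illustration the standard deviation rose by 2 to 4% (0.278 / 0.272 = 1.02; 0.279 / 0.269 = 1.04). If they do not predict it, precision improves (0.252 against 0.264). A baseline value is constant across a participant's sessions, so the retained covariates will change the within-person contrasts very little; omitting them altogether would lose little.

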Oxytocin, Stress, Craving, Opioid Use Disorder (OSCO)

STATISTICAL ANALYSIS PLAN

[name], PhD [name] [contact]; [contact] [contact]

ORIGINAL: 2019 AUGUST 08 REVISED: 2022 MAY 05

Clinical trial registration: Clinicaltrials.gov; NCT04051619

IND/FDA: 135570, oxytocin and yohimbine (Holder: [name])

Table of Contents

Study design, setting and approval	3
Statistical analysis	3
Missing data reporting	4
References	6

Study design, setting and approval

This was a Phase 1, outpatient, randomized, double-blind, cross-over (2x2 design with oxytocin and yohimbine), placebo-controlled, human laboratory study (**Figure 1**). The trial took place at the Center for Alcohol and Addiction Studies, Brown University, Providence, RI, USA from 2019-2023. The clinical protocol was approved by the Brown University Institutional Review Board (IRB), received an FDA Investigational New Drug (IND135570), and was registered on clinicaltrials.gov (NCT04051619). The study was initiated as a between-subjects design. However, following the COVID-19 pandemic, in order to speed up recruitment, the study was changed to a within-subjects crossover design. This modification in the clinical protocol was executed following the FDA Guidance Document on Changes or Modification during conduct of Clinical Investigations ¹. After receiving approval from the Brown University IRB in November 2021, the FDA was notified in an annual progress report and the study design was updated on clinicaltrials.gov in February 2022.

Statistical analysis

For all outcomes, we utilized an intention-to-treat (ITT) approach, where participants were examined based on their *a priori* randomized protocol and received at least one dose of the study medication (oxytocin or oxytocin-matched placebo)²

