- 1. Amount of missing data in the dataset:
 - a. Oxytocin condition: 10% did not receive either oxytocin or placebo condition (within subject, *n*=16; between subject, *n*=4)
 - b. Yohimbine condition: 11.12% did not receive yohimbine condition (yohimbine, *n*=14; placebo, *n*=16; no yohimbine, *n*=4):

- 2. Reason for missing:
 - a. Oxytocin condition: change from between subject to within subject design
 - b. Yohimbine condition: safety concerns due to past history of cardiovascular disease and/or current hypertension (*n*=3), stroke (*n*=1)

3. Consequences:

- a. *Oxytocin condition*: no differences between participants with and without missing values except there were no subject taking methadone in the subjects with missing values.
- b. *Yohimbine condition*: no differences between participants with and without missing values except there were cardiovascular concerns in the subjects with missing values.
- 4. *Method*: GLM with MNAR using all available pairs of data to model missing values with maximum likelihood estimation
- 5. Software: IBM SPSS Statistics for Windows, version 29 (IBM Corp., Armonk, NY, USA)

All statistical analyses were performed after participants had completed their follow-up visits and the study database had been locked. The results were presented using summary statistics: number of subjects (n); mean (M); standard deviation (SD) or frequency distributions (%) and effect size was reported as Cohen's d.

All statistical procedures were performed by IBM SPSS Statistics for Windows, version 29 (IBM Corp., Armonk, NY, USA), and GraphPad Prism (v.10) was used to generate figures (La Jolla, CA, USA). All statistical tests were two-tailed, and statistical significance was accepted if an alpha value p<.05 was obtained.

References

1. FDA. Changes or modifications during the conduct of a clinical investigation; final guidance for industry and CDRH staff. 20012001.

Schulz K, Altman D, Moher D. Consolidated Standards of Reporting Trials Group CONSORT
2010 Statement: Updated Guidelines for Reporting Parallel Group Randomised Trials. Bmj.
2010;340:c332.

4. Tukey JW. The future of data analysis. The annals of mathematical statistics. 1962;33(1):1-67.

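### The outpatient safety outcomes are assigned an ANOVA and a chi-square test with no participant term and no adverse-event counting unit, although 16 of 20 participants supplied both spray conditions

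*SAP*

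**What the plan says.** The SAP (Study design, setting and approval) records that "the study was changed to a within-subjects crossover design". Under Missing data reporting it gives the resulting data structure: "10% did not receive either oxytocin or placebo condition (within subject, *n*=16; between subject, *n*=4".

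The Outcomes paragraph treats two sets of outcomes differently. The laboratory outcomes get a generalized linear model "with medication (oxytocin/placebo) and noradrenergic activation (yohimbine/placebo) as within-subject factors". For the second set, "Other outcomes (safety and tolerability) were measured retrospectively during the one-week outpatient setting"; these are COWS, HAM-A, STAI, PSS, HAM-D and AEs. Their whole analysis is one sentence: "The other outcomes were analyzed using ANOVA test and the number of AEs via a" chi-square test. It does not mention pairing, repeated measures, a participant effect, period, or the unit in which AEs are counted.

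The general rule on significance applies to these tests too: "All statistical tests were two-tailed, and statistical significance was accepted if an alpha value p<.05 was obtained".

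**The concern.** An ordinary chi-square test and a one-way ANOVA assume that every observation comes from a different, independent unit. Here most people appear under both spray conditions. The SAP specifies within-subject factors for the laboratory model and is silent for the outpatient outcomes. Elsewhere it uses chi-square in its ordinary independent-groups sense, to compare enrolled participants with completers.

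What is at stake is the outpatient part of the protocol's Aim 3, safety and tolerability. A conservative test is not cautious in a safety comparison, because it favours a finding of no difference when harm exists. The SAP also says that the within-subjects design optimised power for a modest sample. Tests that ignore pairing give that advantage away for these outcomes. The weight of the point depends on the outcome's status, which the SAP leaves unclear: the sample-size discussion under Statistical analysis labels safety and tolerability primary, and the Outcomes paragraph labels it secondary.

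**Working it through.** **Inputs from the documents.** 16 participants with both spray conditions, 4 with one; two-sided alpha 0.05.

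**Assumptions, because the documents give no figures.** Within-person correlation, AE rates, event dispersion, and (where the four single-condition participants are included) a split of two per condition.

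**1. Reproduce the plan's figure.** Twenty participants and two conditions make 40 participant-condition cells, of which 4 are missing: 4/40 = 10%, as stated. The paired share is 16/20 = 80% of participants, and 32/36 = 89% of the observed condition-periods.

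**2. Scales.** With n pairs and correlation ρ, the variance of the difference in means is 2σ²(1−ρ)/n. A test that ignores pairing uses 2σ²/n. Its true large-sample type I error is therefore P(|Z| > 1.96/√(1−ρ)). At ρ = 0.5 the effective cut-off is 1.96/√0.5 = 2.77, which gives 0.006. Simulation at the actual size (40,000 runs) gives:

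- ρ = 0.5, 16 pairs only: type I error 0.007. Power for a 0.6 SD difference is 0.34.
- ρ = 0.5, 16 pairs plus 2 single-condition participants per condition: type I error 0.011. Power is 0.39.
- A paired test on the 16 pairs at ρ = 0.5: type I error 0.050. Power is 0.62.
- Other correlations, with the four included: unpaired type I error 0.051, 0.023 and 0.003 at ρ = 0, 0.3 and 0.7. At ρ = 0.7 power is 0.38 unpaired and 0.83 paired.

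**3. Participants with at least one AE.** The same algebra holds with the phi coefficient in place of ρ. For phi 0.39 to 0.54 the cut-off becomes 1.96/√0.61 = 2.51 to 1.96/√0.46 = 2.89, which gives 1.2% to 0.4%. Simulation with 16 pairs and phi about 0.4 to 0.5:

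| Test | Type I error, 40% in both | Power, 30% vs 60% |
|---|---|---|
| Pearson chi-square, pairing ignored | 0.6–1.4% | about 38% |
| McNemar, exact | 0.4–0.6% | 31–33% |
| McNemar, mid-p | 1.4–2.3% | 47–50% |

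**4. Total AE events.** With equal exposure the chi-square on totals a and b is (a−b)²/(a+b). Two cases differ sharply.

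- *Events cluster within a participant-period.* If counts have variance-to-mean ratio D and a person's two counts are uncorrelated, the statistic is inflated by D. The false-positive rate is P(|Z| > 1.96/√D). For D = 1.5, 1.96/1.22 = 1.60 gives 11%. For D = 3, 1.96/1.73 = 1.13 gives 26%. Simulation agrees, at about 11 to 25%.
- *Clustering is a stable person effect.* Under the null, each person then has the same event rate in both conditions. Given the total a+b, a is binomial with probability 1/2, so the test is correctly sized. Simulation with 16 pairs gives about 5%. Adding the four single-condition participants raises it to 6 to 7% (person-effect variance 1, mean 1 to 2 events), because their clustering is not shared across conditions.
- *Half the dispersion shared:* 8 to 16%.

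**The case against.** The strongest reply is that the SAP never says its tests are unpaired. Repeated-measures ANOVA is an ANOVA, and McNemar's statistic is referred to a chi-square distribution. The authors plainly knew that the design was a crossover. That much stands: the independent-sample reading is an inference from silence. But the favourable reading leaves a gap too. Standard McNemar and standard repeated-measures ANOVA use complete pairs only, so they would drop the four single-condition participants, whereas the SAP's intention-to-treat statement covers all outcomes and everyone who took at least one dose of spray. On either reading the text does not determine the analysis.

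Three further objections stand and limit the point:

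- **Event counts.** A reader might infer that several events from one person are enough to inflate a chi-square on totals. They are not when that person contributes to both conditions at a stable rate. Inflation needs clustering specific to a participant-period, and the documents offer no evidence on that.
- **Exact McNemar.** At 16 pairs it has less power than the test being criticised, and mid-p McNemar is also below its nominal level. The case for pairing here rests on design and power, not on reaching exactly 5%.
- **Scope.** The sentence covers the outpatient week only. Laboratory blood pressure, heart rate and anxiety are described with the model that has within-subject factors. The SAP also presents the trial as preliminary and ties AE differences to a judgement of clinical relevance, so the AE p-value is not shown to be the sole decision rule.

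**Conclusion.** The point holds for the one-week outpatient safety outcomes. The SAP names methods that, run as written, do not fit a data set in which 80% of participants appear in both conditions, and it leaves the AE counting unit open.

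Two stronger conclusions might be drawn and are not supported. One is that the safety p-values are simply wrong: that depends on how the tests were actually run and on a non-zero within-person correlation, since at zero correlation the unpaired ANOVA is correctly sized (0.051). The other is that the chi-square on AEs is invalid whatever is counted: on event totals it is close to nominal when clustering is a stable person effect.

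Under positive correlation the direction is clear for scales and for any-AE proportions: too conservative, with lost power. The loss is largest for the scales (0.34 to 0.39 against 0.62 at correlation 0.5) and smaller for any AE (38% against 47 to 50% with mid-p McNemar). For event totals the error runs from none to a false-positive rate of about 25%, depending on a dispersion structure that the documents do not describe. All these magnitudes are illustrative.

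**What to change.** Revise the sentence on the other outcomes in the SAP's Outcomes paragraph so that it:

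1. States the AE unit: participants with at least one AE in each condition-period, number of events, or both.
2. Analyses the scales with a linear mixed model, any AE with mixed logistic regression or GEE, and event counts with a Poisson or negative binomial model clustered on participant. Each model should have condition and period terms, so that all 20 participants are kept.
3. Adds sensitivity analyses on the 16 two-condition participants: paired tests for the scales, and mid-p rather than exact McNemar for any AE.
4. Says which tests were in fact run, if results already exist.

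Separately, reconcile the primary label for safety under Statistical analysis with the secondary label under Outcomes. The cost is SAP wording and a re-run on existing data; no new data are needed.
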